Manual examination of histopathological images is labor-intensive and taxing. Moreover, there's a significant risk of overlooking small cancerous regions on slides, especially as malignant cells may be sparsely distributed. In this scenario, machine learning-based automated inspection techniques offer rapid and dependable identification of invasive and noninvasive cancerous cells and regions on the slide. [5] Diagnoses heavily depend on the expertise of medical professionals, introducing subjectivity and limited repeatability, with documented inaccuracies even among experienced practitioners.

Traditional vision screening of histopathological images via light microscopy poses risks of misdiagnosis and struggles with accessibility due to time and personnel limitations. The primary focus is on leveraging advanced computational techniques to automate analysis, addressing inherent drawbacks in traditional screening methods. Through AI approaches, our aim is to create a model surpassing the accuracy of visual assessments, providing a reliable and efficient means of identifying transformation zones and detecting early signs of breast abnormalities. Central to our objective is the recognition of the need for scalable and cost-effective solutions, particularly in low-income settings. The proposed AI model seeks to mitigate the shortage of trained personnel by automating breast cancer histopathological image analysis, streamlining screening and enhancing accessibility. Moreover, we aim to incorporate domain adaptation techniques to ensure the model's precision and resilience across diverse health facilities, considering challenges such as resource constraints, equipment variations, and demographic diversity.

- **Objectives:** Our primary goal is to compile a diverse dataset of breast tissue histopathology images, incorporating samples from various sources to ensure representation across patient demographics and imaging equipment. Using this dataset, we aim to develop a robust AI model for automated classification of invasive and noninvasive breast cancer within histopathology images. Specific objectives include:
 - a) Clinical Validation: Evaluate the AI model's performance through comprehensive clinical validation, measuring sensitivity, specificity, and accuracy in classifying invasive and noninvasive breast cancer types in histopathology images.

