 - b) Usability Assessment: Assess the model's usability by involving healthcare professionals in the evaluation process, measuring integration into clinical workflows, result interpretability, and time efficiency during histopathology examinations.
 - c) Impact on Early Detection: Investigate the AI model's impact on early breast cancer detection, analyzing its contribution to identifying cancer types at earlier stages for potentially improved patient outcomes.
 - d) Generalizability: Evaluate the model's generalizability across diverse datasets, including local sources, assessing its performance in different regions and healthcare settings for broader clinical applicability.
 - e) Impact on Patient Outcomes: Examine the AI model's impact on patient outcomes, such as reduced diagnosis time, increased accuracy in cancer type identification, and enhanced treatment planning, considering potential benefits to patient well-being and satisfaction.
 - f) Clinical Decision Support: Evaluate the model's effectiveness as a clinical decision support tool, measuring its contribution to accurate diagnoses and treatment plans during histopathology examinations.

Through these objectives, our research aims to advance breast cancer diagnosis, providing a comprehensive solution that integrates seamlessly with clinical practices and positively influences patient outcomes.

- **Rationale:** Histopathology images contain valuable information about tissue structure, but manual interpretation can be subjective and time-intensive. Deep learning offers a promising solution by automatically learning complex patterns, potentially improving the accuracy and efficiency of breast cancer classification. This research aims to leverage deep neural networks to analyze extensive datasets of histopathology images, distinguishing between invasive and noninvasive breast cancer with high accuracy. Automating this classification process aims to reduce human error, expedite diagnoses, and support personalized treatment approaches. Ultimately, the goal is to refine breast cancer diagnosis, enabling earlier intervention and better patient outcomes.

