In the retrospective phase of the study, additional data will be retrieved from the clinic's database of prior screenings. Due to the retrospective nature, obtaining consent from individual patients is impractical. To address privacy concerns, any personally identifiable patient information will be systematically excluded from the collected data. This ensures compliance with privacy standards while leveraging valuable information from past screenings. While informed consent cannot be obtained for this dataset, the study will strictly adhere to ethical guidelines and prioritize patient privacy during the data extraction process from the clinic's database.

d) Methods of Data Collection:

- Patient ID (unique identification number)
- Date & Time of data input
- Age
- Histopathological breast image data
- Region of Interest (ROI) Annotations:
 - Lesion size
 - Provisional diagnosis
 - Suggested management (e.g., routine screening, biopsy, etc.)
 - Patient's relevant medical/surgical history
- Additional Information (if available):
 - Relevant diagnostic test results
 - Reproductive history

The hematoxylin and eosin (H&E) stained images obtained from histopathological assessment, along with relevant metadata, will significantly contribute to algorithm design and image analysis. These

images' standard test status and corresponding results will serve as the ground truth for our detection algorithm.

e) **Data Interpretation:** Following the completion of data collection, exploratory data analysis will be conducted to assess patient distribution across various parameters, including transformation zone type, histopathology, and relevant clinical factors. Subsequently, a balanced dataset will be curated to ensure fair representation of image samples.

This curated dataset will serve as the foundation for training and evaluating the artificial intelligence (AI) algorithm developed for automatic classification and detection of abnormalities in histopathological breast screening cases. The trained model will generate predictions regarding the presence or absence of abnormalities in the breast images.

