To validate the accuracy and clinical relevance of the algorithm's predictions, the results will undergo verification and analysis in collaboration with expert histopathologists. Their insights will be invaluable in refining the automatic algorithm, thereby improving its precision in classifying and detecting potential abnormalities during histopathological breast screenings.

f) **Statistical Analysis:** Once the dataset becomes available, statistical analysis will center on evaluating the performance of the developed artificial intelligence algorithms for automatic classification and detection of abnormalities in histopathological breast screening cases. Key metrics such as sensitivity, specificity, precision, recall, F-1 score, and overall accuracy will be utilized for rigorous evaluation. To ensure robustness, experiments involving n-fold cross-validation will be performed, with mean values and standard deviations of performance metrics calculated. This analysis will conclude with a comparative assessment of various deep learning models, assessing their effectiveness in the automatic classification task.

Utilization of Results: The study results will be pivotal in the development and assessment of an automatic detection algorithm for breast cancer screening, with the following primary objectives:

- a) **Automatic Detection:** Evaluate and detect potential abnormalities in histopathological images, furnishing an automated screening tool for efficient identification of breast cancer risk.
- b) **Clinical Decision Support:** Aid healthcare professionals by furnishing an automated analysis to assist in prioritizing treatment strategies and making informed clinical decisions based on the algorithm's findings.

c) Systematic Data Storage: Enable systematic storage of histopathological images and pertinent metadata to bolster ongoing research efforts, all while safeguarding individuals' privacy during the automated detection process.

These outcomes are poised to significantly enhance the efficiency and accuracy of breast cancer screening, offering valuable support to healthcare professionals in Bangladesh.

- **Facilities:** In the case of collecting data from histopathological breast cancer screening, no additional facilities are required except those the clinics are already equipped with (e.g. image acquisition and data storage capacity).

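### One expert review both validates and refines the algorithm on a single dataset, and the protocol does not say which version yields the validation figures

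*Protocol*

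**What the plan says.** Objective a) of the protocol calls for clinical validation, "measuring sensitivity, specificity, and accuracy in classifying invasive and noninvasive breast cancer types in histopathology images".

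Methodology e) (Data Interpretation) describes one balanced dataset: "This curated dataset will serve as the foundation for training and evaluating the artificial intelligence (AI) algorithm". The trained model's predictions are then to be validated: "the results will undergo verification and analysis in collaboration with expert histopathologists". The next sentence gives the same experts a second task: "Their insights will be invaluable in refining the automatic algorithm".

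Methodology f) (Statistical Analysis) centres on "evaluating the performance of the developed artificial intelligence algorithms". For robustness, "experiments involving n-fold cross-validation will be performed, with mean values and standard deviations of performance metrics calculated". The section ends: "This analysis will conclude with a comparative assessment of various deep learning models".

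Objective d) aims at "generalizability across diverse datasets, including local sources" but sets no data aside for that purpose. The protocol names no test set withheld from the review and no point at which a model version is fixed.

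**The concern.** Validation asks how a finished algorithm performs on women who had no part in making it. Refinement uses errors on known women to change the algorithm. Methodology e) has one review do both, on one dataset.

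Cross-validation does not separate the two by itself. It protects the estimate for a fitting procedure settled in advance. Every woman is in a held-out fold once, so every woman's out-of-sample prediction can be shown to the experts and acted on. A later cross-validation of the revised algorithm would reuse the women whose errors led to the revision. Their images and labels would still be left out of the relevant training folds, but the design changes would carry information about them.

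At stake is the meaning of the figures reported under Objective a). The planned output would not let a reader tell a validation estimate from a development estimate.

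**Working it through.** **1. The plan's own precision figure.** Inputs from Methodology b): confidence level 80% (two-sided z = 1.2816), sensitivity and specificity 0.75, margin c = 0.05, prevalence p = 0.261, target N = 500.

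- N_sen = z² × 0.75 × 0.25 / (c² × p) = 1.6424 × 0.1875 / (0.0025 × 0.261) = 471.9. The protocol gives 471 (470.8 with z rounded to 1.28).
- N_spec = 1.6424 × 0.1875 / (0.0025 × 0.739) = 166.7. The protocol gives 166 (166.3 with z = 1.28).

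The stated figures reproduce to rounding, so 0.05 is the planned 80% half-width.

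**2. What all 500 women give.** Expected cancers: 500 × 0.261 = 130.5. Half-width for sensitivity with 130 cancers: 1.2816 × √(0.1875/130) = 0.049, or 4.9 points. The 5-point margin is therefore met only if essentially all the women count as evaluation data. This is for cancer versus non-cancer with every woman scored. It changes with balancing, with leaving out women of unknown test status, and for the invasive versus noninvasive task of Objective a).

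**3. Order of steps.** Side by side, the sections give:

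- e): train and evaluate on one dataset; predictions generated; experts verify them; their insights refine the algorithm.
- f): metrics and n-fold cross-validation for the developed algorithms; comparison of several models.

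Two orders fit this text. In one, the cross-validation is completed on algorithms fixed before the review, and its estimates are not affected by expert feedback. In the other, it is run or repeated after refinement, and they are. The protocol does not choose.

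**4. Illustration of scale (assumed, not derived).** At sensitivity 0.75, missed cancers number 130.5 × 0.25 = 32.6, about 33. Suppose refinement corrects a fraction f of these reviewed misses and nothing carries over to new women. Apparent sensitivity then rises by 0.25 × f:

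| f | Women corrected | Apparent sensitivity | Rise |
|---|---|---|---|
| 10% | 3.3 | 0.775 | 2.5 points |
| 20% | 6.5 | 0.800 | 5 points |
| 50% | 16.3 | 0.875 | 12.5 points |

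The rise equals the planned margin when f = 0.05/0.25 = 20%, about 7 women. Both f and the absence of carry-over are assumptions, and no carry-over is the extreme case. Real improvement in new women would reduce the bias.

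**The case against.** The strongest reply is that the harm depends on steps the protocol does not state. Several stronger readings are tempting, and the document does not support them.

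- *Metrics are re-estimated after refinement.* A reader might infer this because e) precedes f) and f) speaks of developed algorithms. The order of sections is not an order in time, however, and the remark on refinement states an expectation without defining a procedure.
- *The best-scoring model is picked and its score reported.* The text plans a comparison, which can simply mean reporting several models. Any figure for selection bias would need an assumed number of models, a correlation between them and a selection rule, none of which is given.
- *Mean ± SD over folds is the planned confidence interval.* The SD is offered for robustness, not as an interval.
- *The Flow Chart shows that no independent validation will occur.* It is introduced as a data collection timeline, and its last row, on processing and analysis, could include validation. The public data are listed for the initial algorithm, but nothing limits them to that use. Objective d) leaves room for separate testing.

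It can also be said that fold number, grouping, nesting and interval method belong in a statistical analysis plan, which is not shown. For those details alone that is fair.

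What remains is not only missing detail. The protocol itself gives one review of one dataset two purposes that must be kept apart, and says nothing about which algorithm version the Objective a) figures describe. An analysis plan that fixed the algorithm before the review would settle the matter, but it would have to qualify the wording of e).

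**Conclusion.** The concern holds in conditional form. As written, the protocol allows cross-validated figures obtained after expert-driven refinement on the same women to be reported as clinical validation. Such figures would be development performance and would tend to be optimistic. The protocol does not say that this will happen.

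The size of the bias cannot be derived from the document. The 5-point illustration shows only that correcting a small number of women could use up the planned margin. It rests on the protocol's 75% sensitivity and 26.1% prevalence, all 500 women being scored, and two assumptions of this review: one in five misses corrected, and no benefit to new women. The sample size arithmetic itself is not in dispute.

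The protocol should be changed on this point, with medium confidence in its practical effect. The order of steps is cheap to fix beforehand. Once feedback on these women has shaped the algorithm, they cannot give a validation estimate for it.

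**What to change.** In Methodology e) and f), state that:

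- the validation estimates of sensitivity, specificity and accuracy come from out-of-fold predictions, with all images of a woman in one fold, of algorithms fixed before any expert feedback on study patients;
- results of the refined algorithm on the same women are labelled as development results;
- all compared models are reported, or any model choice is nested within the training folds, and the best score is not presented as validation;
- pooled patient-level sensitivity and specificity are given with a confidence interval at the planned 80% level (about ±4.9 points for sensitivity with 130 cancers, if all are scored), restated for the counts actually scored;
- the fold SD is kept only as a description of stability.

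The cost is protocol wording, more computing and possibly lower reported figures; no extra patients are needed. The main drawback is that the refined algorithm has no unbiased estimate until it is tested on new data.

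Reserving study patients for that test would remove the drawback but lose precision. An assumed 20% to 30% hold-out leaves 500 × 0.20 × 0.261 = 26 to 500 × 0.30 × 0.261 = 39 cancers. The 80% half-widths are 1.2816 × √(0.1875/26) = 10.9 and 1.2816 × √(0.1875/39) = 8.9 points, both well outside the planned 5.

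### Nothing separates choosing the model from evaluating it: if the single AI model is picked on the cross-validated results, its reported performance will be biased upward

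*Protocol*

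**What the plan says.** The relevant statements are spread over several sections of the protocol.

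- **Objectives.** The product is singular: "we aim to develop a robust AI model for automated classification of invasive and noninvasive breast cancer". Objective (a) asks for the sensitivity, specificity and accuracy of that model.
- **Methodology e), Data Interpretation.** One dataset has two uses: "This curated dataset will serve as the foundation for training and evaluating the artificial intelligence (AI) algorithm". It is to be balanced. The section then has expert histopathologists review the results and says: "Their insights will be invaluable in refining the automatic algorithm".
- **Methodology f), Statistical Analysis.** The only stated estimator is cross-validation: "experiments involving n-fold cross-validation will be performed, with mean values and standard deviations of performance metrics calculated". The section lists six metrics, of which five are distinct, since sensitivity and recall are the same quantity. The last step of the same analysis is the comparison: "This analysis will conclude with a comparative assessment of various deep learning models".
- **Utilization of Results.** Again one algorithm is the outcome: "The study results will be pivotal in the development and assessment of an automatic detection algorithm for breast cancer screening".

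Two other places might have supplied independent test data. Objective (d) reads: "Evaluate the model's generalizability across diverse datasets, including local sources", but no analysis is attached to it. The Flow Chart uses public data for the initial algorithm in month 1 and does not name them as a test set.

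**The concern.** Several models enter the analysis and one is to come out of it. The cross-validated metrics are the only comparison the protocol provides. They are also its only stated measure of performance. If the same numbers select the model and then describe it, the result is the maximum of several noisy estimates, and that maximum exceeds the true performance of the selected model on average. Ordinary cross-validation does not prevent this. It protects each model from being scored on its own training cases, but not the analyst from choosing the model that was lucky in its scores.

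The answer to objective (a) is at stake. The protocol intends the algorithm to support clinical decisions, and an overstated sensitivity means that more cancers would be missed than the report suggests. No metric is named for ranking the models, so the choice of metric also stays open after the results are seen.

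**Working it through.** **1. The plan's own figure.** Methodology b) gives an 80% confidence level (z = 1.2816), a margin of 0.05, a prevalence of 0.261, and an expected sensitivity and specificity of 0.75.

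- N_sen = z² × 0.75 × 0.25 / (0.05² × 0.261) = 471.9 (470.8 with z = 1.28). Stated: 471.
- N_spec = z² × 0.75 × 0.25 / (0.05² × 0.739) = 166.7 (166.3 with z = 1.28). Stated: 166.

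Both reproduce. The target is 500, so the number of cancers is about 0.261 × 500 = 130.5, taken as 130. The formula treats the 5% as a half-width, so 5 points is the yardstick for any bias.

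**2. Assumptions that the protocol does not give.** K models, with K = 5 or 10. Every model has a true sensitivity and specificity of 75%. The correlation ρ between the models' estimates is 0.5 or 0.8. All 500 patients have a reference result and are scored once, out of fold.

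**3. Winner picked on sensitivity.** The standard error is √(0.75 × 0.25 / 130) = 3.80 points. The expected optimism is SE × √(1 − ρ) × m(K), where m(K) is the expected maximum of K independent standard normals: m(5) = 1.163 and m(10) = 1.539 by numerical integration.

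| K | ρ = 0.5 | ρ = 0.8 |
|---|---|---|
| 5 | 3.80 × 0.707 × 1.163 = 3.1 | 3.80 × 0.447 × 1.163 = 2.0 |
| 10 | 3.80 × 0.707 × 1.539 = 4.1 | 3.80 × 0.447 × 1.539 = 2.6 |

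A simulation with 200,000 runs gives the same values to one decimal.

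**4. Winner picked on overall accuracy.** The standard error of accuracy is √(0.75 × 0.25 / 500) = 1.94 points. With independent errors in sensitivity and specificity, Cov(sensitivity, accuracy) = (130/500) × 0.1875/130 = 0.1875/500 = Var(accuracy). The slope is therefore 1, and sensitivity, specificity and accuracy are all overstated by the same amount, 1.94 × √(1 − ρ) × m(K):

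- K = 5: 1.6 points (ρ = 0.5) and 1.0 (ρ = 0.8).
- K = 10: 2.1 and 1.3.

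The ratio to step 3 is √(130/500) = 0.51, or about half. In step 3, by contrast, only sensitivity and, through it, accuracy are raised; under the same independence, specificity is not.

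**5. What makes it smaller.**

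- *Models that truly differ.* With a true spread of SD 3 points and selection on sensitivity, the optimism is SE²(1 − ρ) / √(SE²(1 − ρ) + 3²) × m(K). For K = 10 this is 2.8 points (ρ = 0.5) and 1.3 (ρ = 0.8).
- *More cancers.* If balancing gave 250 cancers among 500, the SE is √(0.1875/250) = 2.74 points. Selection on sensitivity then gives 2.3 and 1.4 points (K = 5), or 3.0 and 1.9 (K = 10).

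**6. What makes it larger.** If correlations of 0.5 and 0.8 apply to a latent score behind each right-or-wrong call, the estimates themselves are less correlated. With 131 cancers, equal models and selection on sensitivity, simulation gives 3.6 and 2.8 points (K = 5), or 4.8 and 3.8 (K = 10).

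**7. With selection and evaluation separated.** The same simulation with a single model, so with no choice to make, shows no optimism beyond simulation error.

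**The case against.** The strongest reply is that the protocol never says a winner will be picked on its cross-validated score, nor that this score will be the headline. A table of all models side by side carries no selection bias. This stands, and it is why the point is conditional. It does not remove the point: the Objectives require one model, and the protocol offers no other basis for choosing it.

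A second reply is that nesting, the ranking metric and the cut-off rule may be settled in a statistical analysis plan that is not at hand. The text of f) is compatible with nested cross-validation. That is fair for the details. The protocol does, however, fix one dataset, one estimator and a closing comparison within the same analysis, and that structure is what needs the safeguard.

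A reader might infer three stronger things that the documents do not support.

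- *That all models share the same folds in a single-level scheme.* Neither is stated. Using the same patients and the same analysis is enough for the bias.
- *That the optimism uses up most of the 5-point margin.* Under the main assumptions this is clear only with about 10 equally good models, correlation 0.5 and ranking on sensitivity alone. The protocol gives sensitivity no such role.
- *That a planned 80% interval loses its coverage.* The 80% level appears only in the sample size calculation. Section f) plans means and standard deviations, so no result interval has a stated coverage to lose.

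**Conclusion.** The point holds in conditional form. The protocol uses one curated dataset and n-fold cross-validation both to compare models and to report performance, and it does not separate the two uses. If the single model is chosen on these results, its reported performance is biased upward, most strongly on the metric used for the choice.

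Under the main assumptions (130 cancers, all models truly at 75%, correlation 0.5 to 0.8), the overstatement of sensitivity runs from about 1 point (best of 5, picked on accuracy, correlation 0.8) to about 4 points (best of 10, picked on sensitivity, correlation 0.5). True differences between models or more cancers reduce it. Weaker correlation between the estimates increases it. The number of models and the ranking rule are not stated, so no single figure can be given. The direction is upward in every scenario with a choice to make. Expert-led refinement after results are seen is a further source of optimism, which was not quantified.

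**What to change.** In Methodology f), make these changes:

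1. Use nested cross-validation, split by patient so that no patient's images fall on both sides of a split.
2. Choose the model, its tuning and its cut-off in the inner folds only, by one metric named in advance.
3. Report sensitivity, specificity and accuracy from the outer folds, as the performance of the whole selection procedure.
4. Label the other models' figures as descriptive.
5. State that results obtained after the expert-led refinement in e) are exploratory. Nesting does not protect against changes made by people who have seen the results.

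No new data are needed, and all 500 patients stay available for evaluation. A 20% to 30% hold-out would cost more precision: 100 to 150 patients hold about 26 to 39 cancers at a prevalence of 0.261. The 80% half-width for sensitivity, 1.2816 × √(0.1875 / cancers), would then be about 10.9 to 8.9 points against the planned 5.

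The price of nesting is computing time, since every candidate is retrained in the inner folds, and the Flow Chart gives processing and analysis only months 5 and 6. The headline accuracy will also be somewhat lower.
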